3.2 Aims and Objectives

The three specific aims will be realized in the context of the logic model shown in Fig. 3:

AIM 1: Assess the comparative effectiveness of two effective encounter decision aids (Option Grid and Picture Option Grid) against usual care on shared decision-making (SDM), decision quality, treatment choice and other direct outcomes in women, and differentially by socioeconomic status (SES).

Hypothesis 1. The encounter decision aids will increase SDM in the clinic visit and improve decision quality, knowledge, and quality of life in women of higher and lower SES compared to usual care. We also anticipate that they will reduce decision regret and improve the perceived integration of healthcare delivery (see Fig. 3).

Hypothesis 2. The Picture Option Grid will be more effective than the Option Grid at improving primary and secondary outcomes in women of lower SES. There will be no difference between the effects of the two encounter decision aids in women of higher SES.

AIM 2: Measure the effect of the Picture Option Grid on disparities in decision-making (decision quality, knowledge, and SDM) and treatment choice, and conduct an exploratory analysis of the mediation and moderation effects.

Hypothesis 1. Compared to the Option Grid and usual care arms, the Picture Option Grid will reduce disparities in decision quality, knowledge and participation in shared decision-making between women of lower and higher SES. It is also likely to reduce disparities in treatment choice.

Hypothesis 2. The effect of the Picture Option Grid on treatment choice will be mediated by post-intervention knowledge, shared decision-making, and post-intervention values (reported in 'What Matters Most to You' subscale of DQI, e.g., keeping breast, removing breast to gain peace of mind, avoiding radiation, etc.) (see Fig. 4).

[figure not shown]
Hypothesis 3. For women of lower SES, socioeconomic barriers (e.g., resource constraints, as reported in the Decision Quality Instrument) will affect treatment choice and thereby moderate the intervention's effect.

AIM 3: Explore strategies that promote the encounter decision aids' sustained use and dissemination using a theoretical implementation model.

Hypothesis 1. Pre-visit planning, minimal clinician training, flexibility of use, and integration into the workflow and EMR will facilitate sustained use.

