We will adopt a regression framework for all analyses as it allows seamless transition between basic analyses involving a single predictor (or two indicators corresponding to each intervention versus the comparator) and more complex analyses involving additional predictors (mediation variables, control covariates, time-trends, interaction terms or effect modifiers). Further, the regression framework allows clustering of observations due to repeated measurements on patients across time, nesting of health professionals within sites, and patients within health professionals, to be accurately accounted for using mixed-effect regression models¹¹⁷ or generalized estimating equations^{118,119}. Multiple comparisons will be accounted for using Scheffe's method¹²⁰.

The secondary outcomes (SDM, anxiety, integration of healthcare delivery, decision regret, quality of life and financial toxicity) have in excess of 10 levels and will be analyzed as continuous variables. To assess whether the results of each analysis are trustworthy, we will analyze the residuals to check if the assumptions of the model hold¹²¹. For treatment choice, a clearly defined binary variable based on medical record data, we will adapt the model to a logistic regression model.

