A logistic regression model will be used to test for differences in decision quality, knowledge, participation in SDM, and treatment choice between the Picture Option Grid group and the usual care and Option Grid groups, within subpopulations (higher SES versus lower SES). A reduction of disparity due to the interventions will be claimed if the effect of SES on outcomes is significantly smaller for the Picture Option Grid group than for the other two groups at follow-up. As for Aim 1, a linear regression model will be used for the decision quality analysis while an analogous set of other predictors will be included as covariates in the model. The assumptions of the models will be evaluated for adequacy using residual analysis and other model fit diagnostics¹²¹. Our exploratory mediation analyses seek to identify and explicate the mechanism or process that underlies the relationship between the Picture Option Grid and a dependent variable via the inclusion of a third explanatory variable, known as a mediator variable (e.g., knowledge, values, SDM). We are specifically interested in whether interventions operate through the mediator as opposed to directly affecting the outcome. We will perform these analyses even if the findings from Aim 1 and Aim 2 (hypothesis 1) are non-significant in order to determine whether the null effect was due to a null effect of the intervention on the mediator or a null effect of the mediator on the outcome. To determine the generalizability of these mechanisms and identify subpopulations for whom mediation is most pronounced, we will compare the mediation effects across different subgroups (e.g., higher SES versus lower SES).

The traditional and often-used approach to estimating mediation effects is the causal steps approach, which originated in Baron and Kenny (1986)¹²⁴. However, due to the limitations of that approach, we will estimate the mediation effect using the product of coefficients method¹²⁵. Standard errors will be evaluated using the bootstrap¹²⁶ or the PRODCLIN program¹²⁷. Software exists for sensitivity analysis to violations of sequential ignorability and other assumptions required for causality in mediation analyses^{128,129}. We will apply this software and any additional procedures available to our analyses in order to obtain the most robust and defendable results.

4.8.5 Analyses Corresponding to Aim 3

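### For the binary surgery choice, the product of coefficients is not the natural indirect effect, and SES differences in it can reflect scale rather than mechanism

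*Combined protocol and SAP*

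**What the plan says.** Section 3.2 (Aim 2, Hypothesis 2) states: "The effect of the Picture Option Grid on treatment choice will be mediated by post-intervention knowledge, shared decision-making, and post-intervention values". For the outcome, section 4.8.3 says: "For treatment choice, a clearly defined binary variable based on medical record data, we will adapt the model to a logistic regression model". Shared decision-making, one of the mediators, is among the secondary scales that "have in excess of 10 levels and will be analyzed as continuous variables". That rule is written for Aim 1, but it makes a linear arm-to-mediator model the natural reading.

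Section 4.8.4 then says "we will estimate the mediation effect using the product of coefficients method" and "Standard errors will be evaluated using the bootstrap", with PRODCLIN as the alternative. It also says "we will compare the mediation effects across different subgroups (e.g., higher SES versus lower SES", in order to judge how general the mechanisms are and in which groups mediation is strongest. It gives no effect scale for a binary outcome, no standardisation, and no test for the SES comparison.

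The same section notes: "Software exists for sensitivity analysis to violations of sequential ignorability and other assumptions required for causality in mediation analyses". It continues: "We will apply this software and any additional procedures available to our analyses". The plan labels the mediation work exploratory.

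**The concern.** Section 4.8.4 asks two questions: does the intervention act through the mediator or directly, and in which SES group is mediation strongest? With a logistic outcome model, the product answers neither cleanly.

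- **Mediated versus direct.** Log-odds coefficients from models with and without the mediator are not on a common footing, so the product and the direct effect do not sum to the total effect.
- **Higher versus lower SES.** The mediator-to-surgery coefficient is scaled by each group's residual variation, and its absolute meaning depends on the group's mastectomy rate. The protocol itself expects breast-conserving surgery to be less common in lower-SES women (sections 1.2 and 3.1.1).

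At stake is the reading of a stated hypothesis: a gap between SES groups in the product could be reported as a difference in mechanism when it is partly a difference in scale.

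**Working it through.** The plan states no figure for the mediation analysis, so there is none to reproduce. I examined the estimator under the models that the plan implies.

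**Inputs from the documents.** 600 participants, about half in each SES group (4.3.1); three arms, 20% attrition, four surgeons at each of four sites (16), and an ICC of 0.05 for the DQI (4.8.1). Per SES group: 600/2 = 300, or 300 × 0.8 = 240 after attrition.

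**Assumed, not in the documents.** Arm-to-mediator effect a = 0.5 mediator SD; the values of b and c′; mastectomy rates of 10% to 50%; residual SD ratios of 1.5 and 2.

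**Models.** M = aT + e, with e standard normal; logit P(mastectomy) = i + bM + c′T. The natural indirect effect on the risk-difference scale is NIE = mean over e of [expit(i + b(a + e)) − expit(i + be)].

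**1. Units.** a is in mediator units and b is log-odds per mediator unit, so ab is in log-odds.

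**2. Does the product add up?** 2,000,000 simulated patients, i = 0 (50% rate in the comparison arm), c′ = −0.3:

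| b | ab | c′ (fitted) | ab + c′ | total logistic effect |
|---|---|---|---|---|
| −0.8 | −0.401 | −0.300 | −0.701 | −0.615 |
| −1.5 | −0.747 | −0.304 | −1.052 | −0.750 |
| −2.5 | −1.246 | −0.307 | −1.553 | −0.824 |

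At b = −1.5, a mediated share would be 0.747/0.750 = 100%, 0.747/1.052 = 71%, or (total minus direct) 0.445/0.750 = 59%, depending on the definition.

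**3. Dependence on the mastectomy rate** (numerical integration, c′ = 0):

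| Rate | ab when NIE = −4.0 points | NIE when b = −0.5 (ab = −0.25) |
|---|---|---|
| 50% | −0.165 | −5.9 points |
| 30% | −0.205 | −4.8 points |
| 20% | −0.285 | −3.6 points |
| 10% | −0.633 | −2.0 points |

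From 50% to 20% the product for the same absolute effect grows by 0.285/0.165 = 1.73. The last column shows the converse: equal products, unequal absolute effects.

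**4. Dependence on residual variance.** If one group's residual SD is s times the other's, its product is divided by s: 0.5 × (−0.8) = −0.40 becomes −0.267 at s = 1.5 and −0.20 at s = 2. In addition, section 4.8.3 leaves open mixed models (conditional odds ratios) or GEE (marginal odds ratios), which give different values of b.

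**5. How often would a test of the SES difference in ab reject?** 3,000 simulated trials, delta-method z-test at nominal 5%, one third on the Picture Option Grid, no clustering:

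| Scenario | 300 per group | 240 per group |
|---|---|---|
| Rates 40% and 40%, NIE −4.0 in both | 4.1% | 3.6% |
| Rates 50% and 30%, NIE −4.0 in both | 4.4% | 3.4% |
| Rates 50% and 20%, NIE −4.0 in both | 11.3% | 9.3% |
| Rates 50% and 15%, NIE −4.0 in both | 25.7% | 18.7% |
| Residual SD ratio 1.5 | 14.1% | 11.8% |
| Residual SD ratio 2 | 30.0% | 24.2% |

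In the last two rows the groups share the same underlying path (b = −1 before rescaling), but their absolute effects differ too. Those rows show only that a gap in ab need not be a gap in mechanism.

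**6. Clustering.** Analysed patients per surgeon: 600/16 × 0.8 = 30, so about 15 per SES group. Within one SES group, DEFF = 1 + 14 × 0.05 = 1.70 and √1.70 = 1.30. This is the understatement of the first path's standard error if surgeons were ignored and the DQI's ICC applied to the mediator.

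**The case against.** **Scales.** A reader might infer that multiplying a linear path by a logistic path mixes scales. It does not (step 1). The mismatch appears only when the product is set beside the logistic direct or total effect, and the plan does not propose a proportion mediated.

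**False SES differences.** A reader might infer that the comparison will show differences where none exist. The documents do not support that. They give no mastectomy rates, and rejection was near nominal at 50% versus 30%. Whether a difference exists also depends on the scale: with equal products, the log-odds scale shows none and the risk scale shows one. Preferring the risk scale is a choice of estimand, and the contrast in step 3 is not evidence of error.

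**Clustering.** A reader might infer patient-level resampling and a standard error too small by √(1 + 29 × 0.05) = 1.57. The plan does not state a resampling unit. Section 4.8.3 places models with mediation variables in a framework that accounts for patients nested within clinicians, and PRODCLIN can take standard errors from such models. For SES-specific mediation the factor would be about 1.30. For the SES difference no understatement is shown: section 4.8.1 notes that SES varies within physician, so a surgeon effect common to both groups largely cancels.

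**Purpose.** The analysis is exploratory, and one stated use is to tell which path explains a null result. Path coefficients serve that directly.

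All of this stands. What remains is that the plan commits to the product for a logistic outcome and to its SES comparison. The use it names for the causal-mediation software is sensitivity analysis, and a general promise of further procedures fixes no estimand.

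**Conclusion.** The point holds as a minor improvement to an exploratory analysis. For surgery choice, the product is a valid log-odds quantity but not the natural indirect effect. It does not separate mediated from direct effects: the sum overshot the total by 0.09 to 0.73 log-odds in step 2 (0.701 − 0.615 and 1.553 − 0.824), at a 50% rate. SES gaps in it can reflect mastectomy rates or residual variance. With equal absolute effects, rejection for an SES difference ranged from nominal to 25.7% with 300 per group. These sizes rest on assumed rates and path strengths and ignore clustering. They show what can happen, not what will.

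**What to change.** In section 4.8.4, for treatment choice:

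- Make the natural indirect and direct effects on the risk-difference scale the main exploratory mediation estimates, overall and by SES, with an interval for the SES difference. Use the causal-mediation approach already cited there.
- Use mediators measured at T2. The DQI is collected at T2 and T3 (section 4.5.1), and T3 follows the surgery to be explained. CollaboRATE is collected only at T2.
- Keep the path coefficients and their product as a supplement, for locating the source of a null result.
- State that intervals account for clustering by surgeon and, if the bootstrap is used, name the resampling unit.

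The cost is SAP wording; no new data are needed. With about 16 surgeons, roughly five per arm, cluster-based intervals will be wide and approximate. Resampling surgeons within site can lose an arm where a site has only one surgeon in it, so the scheme needs care. Natural effects still require no unmeasured mediator-outcome confounding, which the planned sensitivity analysis should address.

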4.8.6 Secondary Analyses

The consultation recordings and transcriptions will be used to conduct several secondary data analyses:

Cost discussions analysis

In this analysis we will aim to (1) examine the prevalence and characteristics of cost discussions in the surgical consultations (2) investigate whether having a mention of cost in the Picture Option Grid has an effect on cost conversations, the length of the cost

conversation, and whether surgeons make referrals to outside providers or resources for patients to learn more about costs, and (3) study whether patients' financial toxicity, age, race, and/or ethnicity influence our outcomes. Our primary outcome measure will be whether or not cost was discussed in the surgical consultation. Our secondary outcome measures will include who initiated the cost conversations and the length of the conversations, if they occurred. We will also explore the number of times cost was discussed, and whether a referral had been made to address cost.

We will adapt a checklist to analyze the cost discussions from previous published literature and use it to code the recordings.^{134,135} Reviewers will use a combination of audio and transcription files to code each consultation. Two reviewers will dual code a subsample of the recordings, after which kappa and percent agreement will be calculated until kappa reached .75 and percent agreement is over 90%. Once these thresholds are met, the two reviewers will independently code the remaining consultations. A third reviewer will code a 20% subsample of all consultations to ensure consistency.

We will link our analysis with patient-reported demographics (including age, race, and socioeconomic status), patient-reported financial toxicity at one week and 12 weeks post-surgery, and surgery choice as documented in the patient's electronic health record.

We will conduct linear or logistic regression analyses to examine whether our primary and secondary outcomes varied by arm (Picture Option Grid vs. Option Grid and usual care). We will explore whether financial toxicity scores, age, race, or ethnicity influenced our primary outcome. We will also conduct logistic regression analyses to evaluate whether the presence of a cost discussion influenced surgical choice.

Treatment discourse analysis

In this analysis we will aim to (1) examine whether and how breast cancer surgeons give surgical recommendations to early stage breast cancer patients eligible for both lumpectomy and mastectomy, (2) compare surgeon recommendation talk with suggested shared decision making practices, and (3) study the impact effect of clinician decision aid use (Option Grid and Picture Option Grid) on communication, conversational turn-taking, and surgical stance, and overall surgical recommendations. We will compare to usual care in the context of the decision about lumpectomy or mastectomy for early stage breast cancer.

We will analyze a sample of surgical consultations transcripts. Roughly an equal number of transcripts in each group will be coded. We will code transcripts until we reach saturation in themes (estimated at approximately thirty transcripts per arm).

The study team will devise the codebook by adapting the framework developed by Stivers' and Barnes' 2017 paper "Treatment recommendation as actions."¹³⁶ We modified their coding dimensions slightly by removing references to medications, which is not applicable in the breast cancer surgery decision, and removing the "opportunity space" code which identified turn-constructural unit boundaries by conversation analysis. We also added the following codes based on a preliminary review of transcripts: "offers comparable options," "offers time to deliberate," "patient states preferences," and "patient preferences incorporated".

We will code the transcripts using qualitative coding software (NVivo and Atlas.ti) by one researcher with a 20% subsample by a second reviewer. The study team will be available for review when questions or discrepancies arise.

Aberrant transcripts in which only one option was made available by the physician due to imaging or other medical indications (as opposed to physician preference) will be excluded. Codes will be applied according to the agreed upon code description and the context of the transcript. Coding specifics are as follows:

- We will only factors relevant to the breast cancer surgery decision. For example, we will not code detailed information on different types of radiation will, but we will code radiation as a consideration for the lumpectomy decision.
- We will not focus on the surgical logistics after a decision has been made by the patient.
- We will not code standard of care surgical treatments. For example, we will not code details about the sentinel node biopsy (performed during both mastectomy and lumpectomy) because this procedure is standard of care and does not involve comparable options.

We will code all conversations with all clinicians (including surgeons, residents, and medical students) about the early stage breast cancer surgery decision. Conversations between patients and their family members outside of the surgical consultation are occasionally recorded. Although these conversations will not be coded as they are not systematically included for all patients, interesting excerpts about the surgical decision may be marked for later consideration. After reading a transcript, coders will utilize the “memos” feature to document notes and comments on the transcripts.

We will identify major and minor themes from transcripts based on our study framework. We will select representative quotes to illustrate these themes. Additionally, a trained discourse analyst will conduct in-depth analysis of transcripts identified by coders as particularly interesting or representative.

Analysis of spoken plain language

We have three primary aims in this secondary analysis:

1. Qualitatively determine the extent to which clinicians use plain language in the context of breast cancer surgical visits,
2. Quantitatively develop a ‘listenability’ score and determine clinicians’ individual listenability scores to analyze how clinicians communicate with their patients,
3. Compare the qualitative and quantitative results across arms and according to select patient characteristics, and
4. Use existing readability software to analyze the de-identified transcripts for readability scores.

Qualitative analysis

We will use Atlas.ti to conduct a dual independent qualitative analysis of the transcripts. We will perform a deductive analysis using the US federal plain language guidelines¹³⁷⁻¹³⁹. We will develop a codebook from these guidelines as a team, pilot it on 2-3 transcripts, assess for

usability, make necessary changes then code all transcripts. We will also conduct inductive thematic analysis of the transcripts allowing for new codes to emerge as appropriate^{138,140}.

Quantitative analysis

For our quantitative analysis, we will develop a quantitative scoring method, adapted from the Listenability Style Guide and apply it to each recording¹⁴¹. We will then conduct analyses based on listenability scores and participant characteristics. Additionally, we will use readability software on each de-identified transcript to determine the “readability score” of each included transcript.

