12 APPENDIX B. PICTURE OPTION GRID

Early stage breast cancer: What's right for me?

[figure not shown]
Use this **Picture Option Grid** to help you and your healthcare professional decide how best to treat early stage breast cancer (stages I to IIIA). The last page is for **your notes, thoughts, or any questions** for you to discuss with your doctor.

1. Will it affect how long I live?

Lumpectomy with radiation	Mastectomy
	

[figure not shown]
No, how long you live is the same for both surgeries.

2. Will cancer come back in the breast?

Lumpectomy with radiation	Mastectomy
	

Within 10 years, breast cancer returns for about **5-10 in 100 women (5-10%)**.
This depends on the cancer stage and tumor characteristics, rather than on the type of surgery.
Please discuss your individual risks with your doctor.

3. What is removed in the breast?

Lumpectomy with radiation	Mastectomy
	

[figure not shown]
[figure not shown]
Only the cancer lump will be removed.

The whole breast will be removed.

[figure not shown]
Early stage breast cancer: What's right for me?

4. Will I need more than one surgery?

Lumpectomy with radiation	Mastectomy
	
Possibly, 20 in 100 women (20%) might need additional surgery to remove more breast tissue or lymph nodes that have cancer.	Possibly, if your lymph nodes have cancer. Yes , if you choose breast reconstruction.

5. How long will it take me to recover?

Lumpectomy with radiation	Mastectomy
	
Most women are home on the same day as surgery ...but this may vary. It will take about a week, or more, before you can resume usual activities.	...or longer with reconstruction. It will take several weeks, or longer, before you can resume usual activities.

6. Will I need radiation in the breast?

Lumpectomy with radiation	Mastectomy
 	 

Yes, it will mean visits to the hospital **five days a week**, for up to **seven weeks** after surgery.

Radiation is **not usually given** after a mastectomy but may **sometimes** be recommended.

7. Will my lymph nodes be removed?

Lumpectomy with radiation

Mastectomy

Possibly, if cancer spreads to the lymph nodes under your arm. Your doctor will discuss with you whether you should consider further treatment such as surgery or radiotherapy.

8. Will I need chemotherapy and lose my hair?

Lumpectomy with radiation

Mastectomy

You may be offered chemotherapy, but this does not depend on the surgery you choose. Hair loss is common after chemotherapy.

9. How much will it cost?

Lumpectomy with radiation

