Mastectomy

Both options have similar costs.

It is best to know what is covered by your insurance and what your out of pocket costs may be. Don't hesitate to ask your care team about this. They will know who can answer your questions.

Early stage breast cancer: What's right for me?

Notes and questions

Now that you have looked at the Picture Option Grid, this page is for your notes, thoughts or any questions for you to discuss with your doctor.

1. Will it affect how long I live?

6. Will I need radiation in the breast?

2. Will cancer come back in the breast?

7. Will my lymph nodes be removed?

3. What is removed in the breast?

8. Will I need chemotherapy and lose my hair?

4. Will I need more than one surgery?

9. How much will it cost?

5. How long will it take me to recover?

Other questions/thoughts:

Early stage breast cancer: What's right for me?

Editors: [name], [name], [name], [name], [name], [name], [name]

Evidence document: <http://optiongrid.org/cpresources/grid/evidences/9.pdf?x=Z4wDlBhPB>

Publication date: 23 August 2017 Expiry date: 23 August 2019

ISBN: 978-0-9550975-6-0 License: CC BY-NC_ND 4.0 (International)

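### Length and initiator of cost talk are tested by arm only in visits where cost came up, which the Picture Option Grid is itself expected to change

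*Combined protocol and SAP*

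**What the plan says.** Section 4.8.6, under the cost discussions analysis, sets a causal aim: to "investigate whether having a mention of cost in the Picture Option Grid has an effect on cost conversations, the length of the cost" conversation, and on referrals. The outcomes are:

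- Primary: "Our primary outcome measure will be whether or not cost was discussed in the surgical consultation".
- Secondary: "Our secondary outcome measures will include who initiated the cost conversations and the length of the conversations, if they occurred".
- Exploratory: "We will also explore the number of times cost was discussed, and whether a referral had been made to address cost".

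The analysis is stated once for primary and secondary outcomes together: "We will conduct linear or logistic regression analyses to examine whether our primary and secondary outcomes varied by arm". The contrast is the Picture Option Grid against the other two arms combined.

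The two aids differ on cost. Row 9 of the Picture Option Grid (Appendix B) is headed "How much will it cost" and opens with "Both options have similar costs". It then advises the patient to find out what insurance covers and what she may pay herself, and to ask the care team. The Option Grid table in Appendix A has no cost row.

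Section 4.8.6 does not say that a visit without cost talk counts as zero length. It plans no total-duration or two-part analysis, and does not caution that the length comparison depends on something that happens after randomisation.

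**The concern.** Length and initiator exist only in visits where cost was raised, and one arm's material is designed to raise it. The visits with cost talk in the Picture Option Grid arm are then a mixture: those where cost would have come up anyway, and those where the row prompted it. The comparator arms contribute mainly the first kind. A difference in mean length between these sets combines a change in conversations with a change in which visits are counted. The same applies to who initiated, since the row encourages patients to ask.

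At stake is the answer to aim (2). A report could say that the cost row shortened cost conversations when no conversation was shortened and patients heard more about cost overall.

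**Working it through.** The documents give no occurrence rate, duration, spread or number of recordings for this analysis, so there is no stated figure to reproduce. All inputs below are assumptions, varied over a range.

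**Inputs**
- p0: share of visits with cost talk in the comparators (0.20 to 0.50).
- p1: share with cost talk in the Picture Option Grid arm (0.40 to 0.80).
- L0: mean length in the comparators, 120 s.
- d: change in conversations that would have occurred anyway (+15 or +30 s).
- Ls: mean length of conversations that occur only because of the aid (30 to 90 s).

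**Formulas**
- Mean among visits with cost talk, Picture Option Grid arm: [p0(L0 + d) + (p1 − p0)Ls] / p1. Comparators: L0.
- Mean per recorded visit, counting no talk as 0: p0(L0 + d) + (p1 − p0)Ls. Comparators: p0 × L0.
- The conditional contrast is negative, despite d > 0, when p0 × d < (p1 − p0)(L0 − Ls).

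**Central case** (p0 = 0.30, p1 = 0.60, d = +15, Ls = 30)
- Conditional: (0.30 × 135 + 0.30 × 30) / 0.60 = 49.5 / 0.60 = 82.5 s against 120 s, a difference of −37.5 s.
- Per visit: 49.5 s against 0.30 × 120 = 36.0 s, a difference of +13.5 s.
- Effect on conversations that would have happened anyway: +15 s, by construction.
- Reversal threshold: 0.30 × 15 = 4.5 < 0.30 × (120 − Ls), that is, Ls below 105 s.

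**Range (seconds)**

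| p0 | p1 | d | Ls | Difference among visits with cost talk | Difference per visit |
|---|---|---|---|---|---|
| 0.20 | 0.80 | +15 | 30 | −63.8 | +21.0 |
| 0.30 | 0.60 | +15 | 30 | −37.5 | +13.5 |
| 0.20 | 0.40 | +15 | 60 | −22.5 | +15.0 |
| 0.50 | 0.80 | +15 | 60 | −13.1 | +25.5 |
| 0.30 | 0.40 | +30 | 30 | 0.0 | +12.0 |
| 0.40 | 0.50 | +15 | 90 | +6.0 | +15.0 |

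In the last two rows the sign does not reverse: the aid adds few conversations and, in the last, the added ones are fairly long.

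**With no change to existing conversations.** If 20% of visits have 3.0 min of cost talk and the aid adds 1.0-min mentions in another 40%, time per visit goes from 0.2 × 3.0 = 0.60 to 0.60 + 0.4 × 1.0 = 1.00 min. Mean length where it occurred goes from 3.0 to 1.00 / 0.60 = 1.67 min.

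**Simulation of the central case.** 2,000 trials, 100 Picture Option Grid and 200 comparator recordings, lognormal lengths with log-SD 0.6, Welch test, no clustering. The mean conditional difference was −37.2 s, significantly shorter in 71% of trials and significantly longer in none. The mean per-visit difference was +13.6 s, significantly longer in 31%.

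**The case against.** **Length of a conversation is a legitimate quantity.** The aim concerns length per conversation, not minutes per visit, and if prompted conversations are brief then the average one really is shorter. As description this stands. It does not rescue the arm test as an effect of the aid: in the central case the conditional result matches neither the +15 s in conversations that would have occurred anyway nor the +13.5 s per visit.

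**Occurrence is reported alongside.** It is the primary outcome, and the number of mentions is also explored. A careful reader would see occurrence rise next to a shorter mean. This reduces the risk, but length is still tested by arm and no planned analysis combines the two parts.

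**The analysis population is not stated outright.** The qualifier may only note that length exists when a conversation does, and coding zeros is not excluded. The conditional reading is the natural one. If zeros are intended, a sentence settles it.

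**The cost row may prompt long conversations.** Its advice on insurance and personal expenses could do so. This stands as a limit: the reversal needs prompted conversations to be sufficiently shorter.

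**Clustering.** A reader might infer from the bare mention of linear or logistic regression that clustering by surgeon is ignored and false positives inflated. The documents do not support that. Section 4.8.3 adopts one regression approach for every analysis and accounts for patients nested under clinicians with mixed models or GEE. That text sits under Aim 1, so a cross-reference would help. No inflation figure can be attached, because neither the recordings per surgeon nor an ICC for cost talk is given; the 0.05 in section 4.8.1 is for the DQI.

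**Conclusion.** The point holds as a limited one. Testing length and initiator by arm among visits with cost talk conditions on a post-randomisation event that the Picture Option Grid is expected to change, so the contrast can mislead about the aid's effect. Under the assumed inputs the difference among visits with cost talk ran from −63.8 s to +6.0 s in the cases tabulated, while the per-visit difference was positive in all of them.

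A reader might go further and infer that the planned result will have the wrong sign. The documents do not support that: they give no rates or lengths, and the reversal depends on many prompted conversations that are clearly shorter than the others. What is shown is that it can happen under plausible inputs.

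This concerns secondary outcomes of a secondary analysis of recordings. The DQI analysis, the Aim 1 and Aim 2 conclusions and the trial's power are untouched.

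**What to change.** In section 4.8.6, cost discussions analysis:

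1. For the arm comparison, define length as total cost-talk time per recorded visit, 0 where none occurred, over all recorded visits. Because many values will be zero, use robust or bootstrap standard errors, or a two-part model.
2. Replace the single initiator outcome with two, each over all recorded visits: patient-initiated cost talk (yes/no) and clinician-initiated cost talk (yes/no).
3. Report length and initiator among visits with cost talk as description, without an arm test, beside the occurrence result.
4. As a clarification, refer to the mixed-model or GEE handling of clinician clustering in section 4.8.3.

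The cost is SAP wording and one extra analysis on the same coded recordings. The drawback is a zero-heavy outcome with modest power: in the simulation above, the per-visit difference reached significance in 31% of trials. It should be presented with a confidence interval.
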